3.1.4 Post-Treatment Follow-Up and Survival Follow-Up

Patients who complete treatment or discontinue treatment for reasons other than disease progression will undergo assessments (see [Appendix 1](#)) during the post-treatment follow-up period, which will continue until morphologic relapse or up to 2 years, whichever occurs first. Patients who experience morphologic relapse or were followed for 2 years in the post-treatment phase will be evaluated for survival status and

initiation of new anti-leukemia treatment until the end of the study. Details are provided in the schedules of activities (see [Appendix 1](#)).

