4.5.6 Tumor and Response Evaluations

Hematologic malignancy response will be assessed according to ELN and additional response criteria for AML (see [Appendix 19](#)).

Hematologic malignancy response assessments (HMRA) require sampling of blood and bone marrow on the same day as indicated (a window of 4 days is acceptable between the blood and bone marrow sampling). Bone marrow aspirates are required, but if bone marrow biopsies are performed, the biopsy results should be provided along with the aspirate. Depending on the timepoint in the schedule of activities, the HMRA is established on the basis of blood counts only, or includes the assessment of bone marrow. Patients will be considered to be in their best response state until definitive evidence of relapse is available from blood counts, bone marrow aspirate, or bone marrow biopsy.

In the event that a bone marrow aspirate or biopsy is equivocal (i.e., a recovering marrow), the bone marrow assessment and complete blood count should be repeated > 7 days later.

In case disease progression/relapse is determined solely by symptomatic deterioration or by a hematology assessment, a bone marrow aspirate should be performed at that time to complete HMRA. If a patient progresses or relapses outside of the scheduled visit, an unscheduled HMRA must be provided.

If a bone marrow aspirate is performed at any unscheduled timepoint during the study, an unscheduled HMRA must be provided.

Please note that at the time of bone marrow sampling for HMRA, the bone marrow sample collected (aspirate) should also allow for further analyses (e.g., MRD by flow cytometry, MRD by NGS) and the amount taken should be taken into consideration.

During the treatment period, HMRA are to be performed and reviewed before the start of a new treatment cycle. In the event that a patient has a dosing delay > 7 days in consolidation or induction, weekly blood counts must be performed for HMRA to

document evidence of non-progression. Treatment failure and relapse will lead to discontinuation of the study medication and patients will enter follow-up (see [Appendix 1](#)).

During the follow-up of patients who remain in remission after treatment, blood will be required every month and a bone marrow aspirate will be required every 6 months to allow for HMRA until relapse. Refer to [Appendix 1](#) for further details.

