6.3.2 Secondary Efficacy Endpoints

The following secondary efficacy endpoints will be analyzed in patients enrolled during specified phases through use of the same methods described for the primary efficacy endpoint:

Dose-escalation or expansion phase

- Proportion of patients with a CR, CRi, or CRp at the end of induction treatment
- Proportion of patients with a CR or CRh at the end of induction treatment
- Proportion of patients with a negative MRD status at the end of induction treatment

Post-consolidation phase

- Proportion of patients converting from MRD-positive to MRD-negative status at any time during treatment

The following secondary efficacy endpoints will be analyzed in patients enrolled during the dose-escalation and expansion phases:

- EFS, defined as the time from initiation of study treatment (for post-consolidation patients, date of initiation of induction treatment prior to this study) to treatment

failure (failure to achieve CR, CRi, CRp, or CRh), hematologic relapse, or death from any cause, whichever occurs first

Patients with no EFS event at the time of analysis will be censored at the date of last response assessment. Patients with no EFS event and no postbaseline response assessment will be censored at Day 1.

- OS, defined as the time from initiation of study treatment to death from any cause
Patients who have not died at the time of analysis will be censored at the date the patient was last known to be alive.
- RFS in patients who achieve remission (CR, CRi, CRp, or CRh), defined as the time from remission to the date of hematologic relapse or death from any cause, whichever occurs first
Patients with no RFS event at the time of analysis will be censored at the date of last response assessment.

The following secondary efficacy endpoints will be analyzed in patients enrolled during the post-consolidation phase:

- EFS, defined as the time from initiation of induction treatment (prior to study entry) to hematologic relapse or death from any cause, whichever occurs first
Patients with no EFS event at the time of analysis will be censored at the date of last response assessment. Patients with no EFS event and no postbaseline response assessment will be censored at Day 1.
- OS, defined as the time from remission (prior to study entry) to death from any cause
Patients who have not died at the time of analysis will be censored at the date the patient was last known to be alive.

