- RFS in patients who achieved remission (CR, CRi, CRp, or CRh), defined as the time from remission (prior to study entry) to the date of hematologic relapse or death from any cause, whichever occurs first
Patients with no RFS event at the time of analysis will be censored at the date of last response assessment.

The following secondary efficacy endpoint will be analyzed in patients enrolled during all phases:

- Change from baseline in patient-reported disease-related symptoms and health-related quality of life at specified timepoints, as assessed through use of the FACIT-Fatigue, EORTC QLQ-C30 (selected scales), and EORTC Item Library (selected symptoms)

EFS, OS, and RFS will be analyzed descriptively using the Kaplan–Meier method (Kaplan and Meier 1958).

Where medians are reached, the corresponding estimated median will be provided, along with the 95% CI by means of the Brookmeyer and Crowley method (Brookmeyer and Crowley 1982). In addition, when available at the time of the analysis, landmark estimates of the proportion of patients who are event free at 6 months, 9 months, 1 year, and 2 years will be provided, along with 95% asymptotic CIs using Greenwood's formula for standard errors.

Descriptive summary statistics and change from baseline will be calculated at each assessment timepoint for the FACIT-Fatigue, EORTC QLQ-C30 scales, and EORTC Item Library symptoms. Further details of the PRO analyses will be provided in the Statistical Analysis Plan.

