Appendix 1: Schedule of Activities (cont.)

Table 5: Post-Treatment Phase (cont.)

CTCAE=Common Terminology Criteria for Adverse Events; eCRF=electronic Case Report Form; EDTA=ethylenediaminetetraacetic acid; EORTC=European Organisation for Research and Treatment of Cancer; EORTC QLQ-C30=EORTC Quality-of-Life Questionnaire–Core 30; EQ-5D-5L=EuroQol 5-Dimension, 5-Level; FACIT=Functional Assessment of Chronic Illness Therapy; HMRA=hematologic malignancy response assessment; MRD=minimal residual disease; PRO=patient-reported outcome; PRO-CTCAE=Patient-Reported Outcomes Common Terminology Criteria for Adverse Events; Q1M=once a month; Q3M=once every 3 months; Q6M=once every 6 months; Tx=treatment.

- ^a Patients who discontinue treatment for any reasons other than morphological relapse (see Section 4.5.6) will undergo assessments during the post-treatment follow-up period, which will continue until morphological relapse (see Section 4.5.6) or 2 years, whichever occurs first. The first post-treatment follow-up visit is 1 month after the end of drug discontinuation visit.
- ^b Patients who experience morphological relapse (see Section 4.5.6) or ended their 2 years post-treatment follow-up will be evaluated for survival status and new anti-leukemia treatment every 3 months during the survival follow-up period, which will continue until the end of the study.
- ^c For HMRAs during the study, bone marrow aspirates are required, but bone marrow biopsies may be performed at the discretion of the investigator.
- ^d Bone marrow MRD/Flow, EDTA, and PAXgene to be collected at same time as bone marrow for response assessment. If unscheduled bone marrow aspirate is being collected for hematologic response assessment, then bone marrow MRD/Flow, EDTA, and PAXgene samples should also be collected. If any MRD assessments are done locally, please record this information in the eCRF. The priorities are MRD/FLOW > EDTA > PAXgene.
- ^e PRO questionnaires need to be self-administered before the patient receives any information on disease status. Completion of PROs should occur prior to the performance of non-PRO assessments whenever possible. PRO assessments include the FACIT-Fatigue, EORTC QLQ-C30, EORTC Item Library symptoms, PRO-CTCAE, and EQ-5D-5L.

Appendix 2

Schedule of Pharmacokinetic and PD Biomarker Samples

Table 1 All Cohorts

| Study Visit | | Plasma Idasanutlin PK Sample | Serum MIC-1 Sample | Plasma Cytarabine PK Sample | Plasma Daunorubicin PK Sample |

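### EFS and RFS count deaths after scheduled response assessment has stopped but censor survivors earlier, so a late death can take the curve to zero, mainly in the post-consolidation cohort

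*Combined protocol and SAP*

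**What the plan says.** Section 6.3.2 takes as the closing events for EFS and RFS "hematologic relapse or death from any cause, whichever occurs first" (plus treatment failure for EFS in the dose-escalation and expansion phases). It sets no limit on how long after the last assessment a death may fall. For EFS, "Patients with no EFS event at the time of analysis will be censored at the date of last response assessment"; for RFS, "Patients with no RFS event at the time of analysis will be censored at the date of last response assessment".

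Section 3.1.4 sets the post-treatment assessment period, "which will continue until morphologic relapse or up to 2 years, whichever occurs first". After that, Appendix 1, Table 5, footnote b says patients "will be evaluated for survival status and new anti-leukemia treatment every 3 months during the survival follow-up period", and this runs to the end of the study. Table 5 schedules no response assessment in that period.

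Section 4.5.6 words the follow-up differently: "a bone marrow aspirate will be required every 6 months to allow for HMRA until relapse". It does not repeat the 2-year limit, though it refers to Appendix 1, which has it. It also requires an unscheduled response assessment when a relapse is found between visits.

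The planned outputs are descriptive: Kaplan-Meier curves, the median where reached, and landmarks at 6, 9, 12 and 24 months.

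**The concern.** Take two patients in remission when scheduled assessment ends. One lives to the data cut-off and is censored back at the last response assessment. The other dies a year later and stays in the risk set until that death. Whether a patient is at risk in the late period thus depends on a future event, which Kaplan-Meier does not allow. Past the latest censoring time of any survivor, the risk set consists only of patients who will die. The last of them is at risk alone, and that death takes the estimate to zero.

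At stake are the tail of the curve and the median. Because a median is reported whenever the curve crosses one half, a cohort with more than half its patients event-free could be given a median that comes only from the follow-up schedule. Relapses after the 2-year point are also not systematically looked for, so some could first appear in EFS or RFS as a death.

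**Working it through.** The plan states no event count, power or expected median for EFS or RFS, so there is no figure to reproduce.

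**1. Timeline** (cycle lengths and day limits from Appendix 1, 12 maintenance cycles, 2-year assessment cap, study length about 72 months; 30.44 days per month)

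- Full course in 28-day cycles: (2 + 4 + 12) x 28 = 504 days = 16.6 months.
- Full course at the longest cycle limits: 2 x 56 + 4 x 49 + 12 x 28 = 644 days = 21.2 months.
- Post-consolidation: 12 x 28 = 336 days = 11.0 months.
- Adding 24 months, scheduled assessment ends 40.6, 45.2 and 35.0 months after first study dose.
- Deaths-only follow-up for a patient enrolled at month 0: 72 - 40.6 = 31.4, 72 - 45.2 = 26.8 and 72 - 35.0 = 37.0 months.
- For a full-course expansion patient enrolled at month 18 or 24 (assumed start of expansion): 54 - 40.6 = 13.4 or 48 - 40.6 = 7.4 months.

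**2. Worked example.** S(t) is the product of (1 - d/n) over event times. Take 20 patients: 10 events by month 22, 9 survivors last assessed at months 30-45, and one death in remission at month 60.

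- As written: 0.50 x (1 - 1/1) = 0.
- Late death censored at the last assessment: the curve stays at 0.50.
- If relapse assessment had continued, with all 10 at risk at month 60: 0.50 x (1 - 1/10) = 0.45.

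With 8 early events instead, the rule as written takes the curve from 0.60 to 0 and gives a median of 60 months. With the late death censored, the median is not reached.

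**3. Simulation.** 4000 trials per setting, analysis at month 72. All of the following are assumptions: uniform accrual over the stated months, 30-50% never relapse, median time to relapse 10 months in the rest, death without relapse 1-5% per year, median survival after relapse 8 months.

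| Cohort and accrual | Late death takes curve to 0 | Drop also creates a median |
|---|---|---|
| Post-consolidation, n=30, months 0-24 | 65-87% | 0.3-26% |
| Post-consolidation, n=30, months 0-48 | 43-68% | 0.6-21% |
| n=20, months 0-48 | 19-38% | 0.4-9% |
| n=20, months 12-48 | 10-20% | 0.4-6% |

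The spurious median depends most on the share who never relapse. In the first row it is 0.3-1.8% when that share is 30% and 11-26% when it is 50%.

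**4. Runs that respect the order of the phases** (expansion starting at year 1.5-2; start date and event rates again assumed)

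- Post-consolidation: zero curve in about 49-84%, against 0% with truncation; spurious median about 13-22%.
- Favorable/intermediate: about 3-11%. With about 55% never relapsing, a spurious median arose in about 0.5-1.6%.
- High-risk: about 4-11%, against 3-6% with truncation; no spurious medians were seen.

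**The case against.** Censoring at the last response assessment is a common convention, and EFS and RFS here are descriptive secondary endpoints with no test and no comparison between cohorts. Both points stand. They limit the seriousness but do not remove the fault, which lies in joining that convention to unlimited late deaths.

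A reader might infer that all three cohorts are hit equally. The documents do not support that. Section 3.1.1 opens the expansion phase only after dose escalation is complete, and Section 3.2 ends follow-up 2 years after the last enrolment, so late entrants have little or no deaths-only time. The 19-38% for n=20 in the table needs accrual from month 0 and should not be applied to the expansion cohorts. Escalation patients treated at the RP2D are pooled into the favorable/intermediate cohort (Section 6.3) and raise its figure somewhat.

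A reader might also infer that every relapse after year 2 is lost. That is too strong: Section 4.5.6 requires an unscheduled assessment when relapse is found, and the 3-monthly record of new anti-leukemia treatment can reveal one. Living event-free patients would still be censored at their last assessment.

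Finally, no analysis date is fixed. With analysis at year 5 and late expansion accrual, the stated rule and truncation gave about the same favorable/intermediate result (5-6% each).

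**Conclusion.** The concern holds for the tails and medians of EFS and RFS. It matters mainly for the post-consolidation cohort, which enrols in parallel with dose escalation: roughly 50-85% of simulated curves reach zero, against about 0% with truncation, and roughly 13-22% show a spurious median. For the expansion cohorts the effect is modest (roughly 3-11% and 4-11%), with few or no spurious medians, and in the high-risk cohort truncation removes only part of it.

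The mechanism follows from the text and needs no assumption. The percentages rest on assumed accrual, relapse, cure and death rates and on analysis at year 6. The spurious-median figure also requires that about half the patients never relapse.

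Landmarks up to 2 years are essentially unaffected, because response assessment continues for up to 2 years after treatment stops. OS and the primary CR endpoint are also essentially unaffected. The point should be corrected before EFS or RFS is analysed, but it does not threaten the main conclusions.

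**What to change.** In Section 6.3.2, truncate EFS and RFS at the end of each patient's scheduled response follow-up. Count a death as an event only if it falls within that period; otherwise censor at the last response assessment. OS keeps all deaths. An analysis of EFS and RFS with all deaths may be shown as a sensitivity analysis. It is worth having, because some excluded deaths may follow an undetected relapse and leaving them out favours the treatment.

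A rule that counts deaths within 6 months of the last assessment should not be used instead. It still censors survivors at that assessment and so recreates the asymmetry: post-consolidation curves still reached zero in about 17-32% of simulated trials.

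Section 4.5.6, which describes assessment until relapse, must be reconciled with the 2-year limit in Section 3.1.4 and Appendix 1, Table 5, because the truncation point depends on it.

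The cost is a change to protocol wording in Section 6.3.2 and the reconciliation of Section 4.5.6. A few late deaths leave EFS and RFS but remain in OS.

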- RFS in patients who achieve remission (CR, CRi, CRp, or CRh), defined as the time from remission to the date of hematologic relapse or death from any cause, whichever occurs first

Post-consolidation phase

- Proportion of patients converting from MRD-positive to MRD-negative status at any time
- EFS, defined as the time from initiation of induction treatment (prior to study entry) to hematologic relapse or death from any cause, whichever occurs first
- OS, defined as the time from remission (prior to study entry) to death from any cause
- RFS in patients who achieved remission (CR, CRi, CRp, or CRh), defined as the time from remission (prior to study entry) to the date of hematologic relapse or death from any cause, whichever occurs first

All phases

- Change from baseline in patient-reported disease-related symptoms and health-related quality of life at specified timepoints, as assessed through use of the Functional Assessment of Chronic Illness Therapy (FACIT)-Fatigue, European Organisation for Research and Treatment of Cancer Quality-of-Life Questionnaire, Core 30 (EORTC QLQ-C30) (selected scales), and European Organisation for Research and Treatment of Cancer (EORTC) Item Library (selected symptoms)

The exploratory efficacy objectives for this study are as follows:

- Primary and secondary endpoints (defined above) in the subset of patients with wild-type p53
- MRD response over time (i.e., during induction, consolidation, and maintenance)

- Time to MRD-negative status, defined as time from initiation of treatment to confirmation of negative MRD status

The pharmacokinetic (PK) objectives for this study are as follows:

- To characterize the PK profiles of idasanutlin (and its metabolites, if appropriate), cytarabine, and daunorubicin on the basis of the following endpoint:
 - Plasma concentration of idasanutlin (and metabolites, if appropriate), cytarabine, and daunorubicin at specified timepoints
- To assess potential PK interactions among idasanutlin, cytarabine, and daunorubicin on the basis of the following endpoint:
 - Plasma concentration of idasanutlin (and metabolites, if appropriate), cytarabine, and daunorubicin at specified timepoints

The exploratory PK objective for this study is to evaluate potential relationships between drug exposure and the efficacy and safety of idasanutlin, cytarabine, and daunorubicin on the basis of the following endpoints:

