2.2.2 Secondary Efficacy Objectives

The secondary objective for this study is to evaluate the efficacy of idasanutlin when given in combination with cytarabine and daunorubicin as induction treatment, in combination with cytarabine as consolidation treatment, and/or as a single agent during maintenance treatment, on the basis of the following endpoints, which will be analyzed in patients enrolled during specified phases:

Dose-escalation or expansion phase

- Proportion of patients with a CR, complete remission with incomplete blood count recovery (CRi), or complete remission with incomplete platelet count recovery (CRp) at the end of induction treatment
- Proportion of patients with a CR or complete remission with partial hematologic recovery (CRh) at the end of induction treatment
- Proportion of patients with a negative MRD status at the end of induction treatment
- EFS, defined as the time from initiation of study treatment to treatment failure (failure to achieve CR, CRi, CRp, or CRh), hematologic relapse, or death from any cause, whichever occurs first
- OS, defined as the time from initiation of study treatment to death from any cause
- RFS in patients who achieve remission (CR, CRi, CRp, or CRh), defined as the time from remission to the date of hematologic relapse or death from any cause, whichever occurs first

Post-consolidation phase

- Proportion of patients converting from MRD-positive to MRD-negative status at any time
- EFS, defined as the time from initiation of induction treatment (prior to study entry) to hematologic relapse or death from any cause, whichever occurs first
- OS, defined as the time from remission (prior to study entry) to death from any cause
- RFS in patients who achieved remission (CR, CRi, CRp, or CRh), defined as the time from remission (prior to study entry) to the date of hematologic relapse or death from any cause, whichever occurs first

All phases

- Change from baseline in patient-reported disease-related symptoms and health-related quality of life at specified timepoints, as assessed through use of the Functional Assessment of Chronic Illness Therapy (FACIT)-Fatigue, European Organisation for Research and Treatment of Cancer Quality-of-Life Questionnaire, Core 30 (EORTC QLQ-C30) (selected scales), and European Organisation for Research and Treatment of Cancer (EORTC) Item Library (selected symptoms)

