6.3 EFFICACY ANALYSES

Efficacy analyses will be performed including all patients who received at least one dose of any study drug given in combination or as a single agent.

Data from patients enrolled during the dose-escalation phase will be analyzed separately, by dose. Data from patients who were treated at the RP2D during the dose-escalation phase will be pooled with the corresponding cohort of the expansion phase (favorable/intermediate cohort). Data from the favorable/intermediate cohort, high-risk cohort (expansion phase), and post-consolidation cohort will be analyzed separately, without direct comparison among cohorts. Response definitions used in the section below are provided in [Appendix 19](#).

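### Post-consolidation EFS, RFS and OS start before study entry, so their Kaplan–Meier estimates count time that is event-free by selection

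*Combined protocol and SAP*

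**What the plan says.** Three time-to-event endpoints are defined for the post-consolidation cohort in the Synopsis, Section 2.2.2 and Section 6.3.2.

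- EFS: "EFS, defined as the time from initiation of induction treatment (prior to study entry) to hematologic relapse or death from any cause".
- OS: "OS, defined as the time from remission (prior to study entry) to death from any cause".
- RFS: the same remission origin as OS, with relapse or death as the event.

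Section 6.3.2 analyses all three by ordinary Kaplan–Meier, with medians, and adds that "landmark estimates of the proportion of patients who are event free at 6 months, 9 months, 1 year, and 2 years will be provided". It mentions neither delayed entry nor an analysis from first dose. A patient with no EFS event and no post-baseline assessment is censored at Day 1, which is not defined for this cohort. The EFS bullet for the dose-escalation and expansion phases also carries a parenthesis, "for post-consolidation patients, date of initiation of induction treatment prior to this study". That bullet counts treatment failure as an event; the cohort's own EFS definition does not.

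Section 6.3 analyses "all patients who received at least one dose of any study drug". Section 4.6.1 replaces post-consolidation patients who stop before a first idasanutlin dose.

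MRD conversion is worded as "Proportion of patients converting from MRD-positive to MRD-negative status at any time" in the Synopsis and Section 2.2.2, and as "Proportion of patients converting from MRD-positive to MRD-negative status at any time during treatment" in Section 6.3.2. None of the three names the baseline sample.

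**The concern.** Section 3.3.2 says this cohort is there to assess the safety and benefit of maintenance. The study drug begins only after off-study induction and consolidation, yet the survival clocks begin months earlier. A patient who relapsed or died in between could not have joined the cohort. That interval therefore adds event-free time to every patient's record, whatever idasanutlin does, and the amount depends on the treatment received outside the study.

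The cohort is single-arm, so readers will set its medians and landmarks beside whatever maintenance data they know. The different origins also make the endpoints incoherent with each other: a patient who dies without relapse has a longer EFS than OS.

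**Working it through.** **1. Can an event occur before the first dose?** The inclusion criterion in Section 4.1.1.3 speaks of remission after induction, so it does not settle the question alone. Table 3, Section 3.3.2 and Section 6.1 describe the cohort as being in remission when enrolled. Together with the dosed-only analysis set (Section 6.3) and replacement of undosed patients (Section 4.6.1), this excludes both death and relapse between the origin and first dose.

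**2. Length of the lead-in (illustration).** The plan gives no figure to reproduce, because off-study cycles are not capped. As a proxy I use this protocol's nominal 28-day cycles (Appendix 1, Tables 1 and 2: up to 2 induction and up to 4 consolidation cycles). I add 0 to 21 days between the end of consolidation and first dose (Section 4.1.1.3), date remission at the end of induction, and take a month as 30.44 days.

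- EFS, shortest: 28 + 28 = 56 days = 1.84 months.
- EFS, longest: 2×28 + 4×28 + 21 = 189 days = 6.21 months.
- OS and RFS, shortest: 28 days = 0.92 months.
- OS and RFS, longest: 4×28 + 21 = 133 days = 4.37 months.

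**3. Effect on the estimates.** Assume an exponential time to event from first dose with median M. With lead-in L, Kaplan–Meier from the plan's origin estimates S(t) = 0.5^((t − L)/M) for t > L, and 100% before that. If all patients share L, the median becomes M + L.

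12-month estimates (%):

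| M (months) | From first dose | EFS, L = 1.84 | EFS, L = 6.21 | RFS, L = 0.92 | RFS, L = 4.37 |
|---|---|---|---|---|---|
| 9 | 39.7 | 45.7 | 64.0 | 42.6 | 55.6 |
| 12 | 50.0 | 55.6 | 71.6 | 52.7 | 64.4 |
| 18 | 63.0 | 67.6 | 80.0 | 65.3 | 74.5 |

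At M = 12, the 24-month EFS of 25.0% would read 27.8–35.8%. The 6-month EFS of 70.7% would read 78.6% at the shortest lead-in and 100% at the longest, where the landmark falls before the first dose.

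**4. Mixed lead-ins.** Not every patient will have the longest lead-in. With L uniform on 1.84–6.21 months and M = 12, the mean of 2^(L/12) is 12/(0.693×4.37) × (1.431 − 1.112) = 1.265. Then 12-month EFS is 0.5×1.265 = 63%, and the median solves 2^(m/12) = 2×1.265, giving m = 16.1 months. A simulation gave the same values (63.3% and 16.1 months).

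**5. EFS against OS.** For a death without relapse, EFS minus OS is the time from start of induction to remission: 28 to 2×28 = 56 days on nominal cycles.

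**6. MRD denominator.** Positivity at screening is not required for entry. Suppose 20–50% of the 30 patients are flow-negative at screening (an assumption; no figure is given). With a screening baseline they cannot convert, so a true 40% conversion among the rest would read 0.40×0.80 = 32% down to 0.40×0.50 = 20% on all 30. Restricting to baseline-positive patients leaves 30×0.80 = 24 down to 30×0.50 = 15. Exact 90% Clopper-Pearson intervals (the method returns 49–86% for 14/20, as in Table 14) are 25–57% for 12/30, 25–60% for 10/24 and 19–64% for 6/15.

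**The case against.** The strongest reply is that nothing is hidden. The origins are stated in three places, the endpoints are secondary and descriptive, Section 6.3 rules out direct comparison among cohorts, and Section 4.5.2 collects prior-treatment dates, so first-dose estimates could be produced anyway. All of that stands, and it means this is not an error-rate or power problem. But disclosure does not turn a curve measured from off-study induction into a description of maintenance.

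It can also be said that the origins parallel those of the other cohorts. They do in form, but those patients receive idasanutlin from induction onward, so their EFS starts with study treatment. Here it does not.

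A third reply is that the earlier origins could be kept with delayed-entry risk sets. That is correct, and it is allowed for in the fix; the plan does not specify it.

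Two stronger readings are tempting and should be resisted.

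- A reader might infer a much longer lead-in by running every off-study cycle to the Day 56 and Day 49 limits in Appendix 1. Those limits govern when end-of-cycle assessments are repeated in this study's own induction and consolidation. They say nothing about outside regimens.
- A reader might infer that the local end-of-induction MRD result is the conversion baseline, so that patients cleared by consolidation chemotherapy would count as converters on an inactive drug. The text leans the other way. Section 6.3.2 restricts conversion to the treatment period, and Appendix 1, Table 4 (footnote a) accepts prior results as baseline only within the screening window of Days –14 to –1. What remains is an unnamed sample, looser wording in the Synopsis and Section 2.2.2, and an all-treated denominator.

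**Conclusion.** The time-origin concern holds. The direction of the bias needs no assumption: post-consolidation EFS, RFS and OS are overstated as descriptions of maintenance. The size is not fixed by the documents. It depends on the outside treatment actually given and, in the table above, on exponential event times with an assumed median. At a 12-month median from first dose, 12-month EFS of 50% would read 56–72% (about 63% with mixed lead-ins), and 12-month RFS of 50% would read 53–64%. The primary endpoint and the other cohorts are unaffected.

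The MRD point is narrower: a clarification of baseline sample, denominator and wording, not evidence that the plan would credit idasanutlin with earlier clearance.

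**What to change.** **Time origins.** In the Synopsis, Section 2.2.2 and Section 6.3.2, start this cohort's EFS, RFS and OS at the first idasanutlin dose. EFS and RFS then coincide, so report them once. Keep any induction- or remission-origin analysis as supplementary only, with delayed entry (left truncation) at first dose; without it the same bias remains. Remove the post-consolidation parenthesis from the dose-escalation and expansion EFS bullet. State that Day 1 in the censoring rule is the first maintenance dose, which fits the Day 1 column of Appendix 1, Table 4.

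**MRD conversion.** Name the screening flow-cytometry result as baseline and report conversion among patients positive on it. List separately those who are flow-negative or not evaluable at screening. Note that some of the flow-negative patients may differ only by assay, since eligibility rests on a local method (Section 4.1.1.3) and study MRD is primarily flow (Section 3.3.4.2). Use one wording in all three places.

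**Cost.** The change is mostly wording: prior-treatment dates and the screening marrow are already collected. EFS and RFS cease to be separate endpoints in this cohort. The MRD denominator shrinks, to 24–15 under the assumed 20–50%, with the wider intervals shown above. Because flow is second in sample priority at screening (Appendix 1, Table 4, footnote n), missing baseline results could reduce it further.
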